20.0 Confidentiality*

A. Confidentiality of Study Data

Describe the local procedures for maintenance of confidentiality of study data and any records that will be reviewed for data collection.

*20.1 A. Where and how will all data and records be stored? Include information about: password protection, encryption, physical controls, authorization of access, and separation of identifiers and data, as applicable. Include physical (e.g. paper) **and** electronic files.*

Response:

Identifiers will be collected on the Demographics page of the Baseline form. This form will be kept in a locked cabinet in the PI's office. This form will contain the Study subject ID number and their initials. All subsequent forms will only contain the Subject Study ID number and their initials.

Subjects will be asked to provide personal health information (PHI). All attempts will be made to keep this PHI confidential within the limits of the law. However, there is a chance that unauthorized persons will see the subject's PHI. All study records will be kept in a locked file cabinet in the PIs office. Electronic files will be password protected.

Any publications from this trial will not use information that will identify subjects by name. Organizations that may inspect and/or copy research records maintained at the participating site for quality assurance and data analysis include groups such as the IRB, Sponsor and the pertinent regulatory authorities.

20.2 A. How long will the data be stored?

Response: Data will be stored for the duration of this study and up to ten years after procurement.

20.3 A. Who will have access to the data?

Response: Only members of the PI's research team will have access to the data obtained from participants. De-identified data will be made available to the broader scientific public per FDA policy.

20.4 A. Who is responsible for receipt or transmission of the data?

Response: The co-PIs are responsible.

20.5 A. How will the data be transported?

Response: The paper data collection forms will be transported by the research personnel in subject specific manila folders to the PIs office where they will be stored under lock and key.

B. Confidentiality of Study Specimens

Describe the local procedures for maintenance of confidentiality of study specimens.

N/A: No specimens will be collected or analyzed in this research.
(*Skip to Section 19.0*)

20.6 B. Where and how will all specimens be stored? Include information about: physical controls, authorization of access, and labeling of specimens, as applicable.

Response: Specimens will be stored in -80°C freezers in the laboratory of the Co-I in the Clinical and Translational Research Center where access is restricted to building employees only. Specimens labels will only have the study subject number and therefore will be coded.

20.7 B. How long will the specimens be stored?

Response: All coded specimens will be stored for the duration of this study and up to ten years after procurement.

20.8 B. Who will have access to the specimens?

Response: Only members of the PI's research team will have access to the specimens obtained from participants.

20.9 B. Who is responsible for receipt or transmission of the specimens?

Response: Saliva specimens collected up to Day 28 will be transported by courier to the CTRC and received by [name], the co-I.

20.10 B. How will the specimens be transported?

Response:

Saliva Specimens will be transported from the subject's home to the CTRC by Courier. The subject will be instructed to place the collected saliva specimens in a biohazard bag and then store them in their home refrigerator/freezer. The specimens will be provided to the courier who will bring them to the laboratory in a thermacol box that contains ice pack or dry ice.

21.0 Provisions to Monitor the Data to Ensure the Safety of Subjects*

N/A: This study is not enrolling subjects, or is limited to records review procedures only. This section does not apply.

NOTE: Minimal risk studies may be required to monitor subject safety if the research procedures include procedures that present unique risks to subjects that require monitoring. Some examples include: exercising to exertion, or instruments that elicit suicidality or substance abuse behavior. In such cases, N/A is not an acceptable response.

21.1 Describe the plan to periodically evaluate the data collected regarding both harms and benefits to determine whether subjects remain safe.

Response: On a weekly basis the co-PIs will review the data being collected to determine if there are any worrisome patterns of the adverse events (grade 3 or 4) and SAEs reported. This review will be blinded. We do anticipate a 20% rate of hospitalization in our subjects. Therefore, only if the rate is much higher than that will there be a cause of concern.

21.2 Describe what data are reviewed, including safety data, untoward events, and efficacy data.

Response: All safety data will be reviewed.

External Review of Data

[name], an infectious disease specialist at University of Buffalo will serve as an external reviewer for the outcomes collected in this study. Specifically, he will adjudicate whether the adverse events (grade 3 or 4) and SAEs collected are drug or disease related. He will also adjudicate whether the hospitalizations observed in this study were COVID related or not. These adjudications will be on blinded data.

21.3 Describe any safety endpoints.

- Response: Cumulative incidence of serious adverse events (SAEs)
 - Cumulative incidence of Grade 3 and 4 adverse events (AEs).
 - Adverse effects of special interest: Anxiety and Depression (GAD-2 and PHQ-2 questionnaires); Drowsiness (will be recorded)
 - Discontinuation or temporary suspension of the investigational medication (for any reason).

21.4 Describe how the safety information will be collected (e.g., with case report forms, at study visits, by telephone calls with participants).

Response: The safety information will be collected by scheduled phone calls as described above.

21.5 Describe the frequency of safety data collection.

Response: Days 1, 3, 7, 14, 28 and 42

21.6 Describe who will review the safety data.

Response: The co-PIs will review the data along with the biostatistician [name].

21.7 Describe the frequency or periodicity of review of cumulative safety data.

Response: Weekly

21.8 Describe the statistical tests for analyzing the safety data to determine whether harm is occurring.

Response: As the number of participants is small and data is blinded, formal statistical testing will not be used.

21.9 Describe any conditions that trigger an immediate suspension of the research.

Response: A hospitalization rate that is much larger than the anticipated 20%. A high incidence of adverse events that can be potentially attributed to Melatonin.

22.0 Withdrawal of Subjects*

- N/A:** This study is not enrolling subjects. This section does not apply.

*22.1 Describe **anticipated** circumstances under which subjects may be withdrawn from the research without their consent.*

Response: If they have adverse events that could be possibly related to Melatonin such that the study team think their continued participation is not advisable. If participants are noncompliant with the research procedures, there is the possibility they will be withdrawn from the research.

For those subjects that have not had a previous tests, once enrolled if the subject is found to be COVID-19 negative by EUA rapid antigen testing, the subject will be withdrawn from the study.

22.2 Describe any procedures for orderly termination.

NOTE: Examples may include return of study drug, exit interview with clinician. Include whether additional follow up is recommended for safety reasons for physical or emotional health.

Response: An end of study visit will be conducted over the phone and a courier will be sent to pick up study materials and samples.

22.3 Describe procedures that will be followed when subjects withdraw from the research, including retention of already collected data, and partial withdrawal from procedures with continued data collection, as applicable.

Response: Subjects who withdraw from taking the study drug will be encouraged to stay in the study. If they choose not to, a telephonic end of study visit and courier collection of samples and study materials will be done. Already collected data and samples will not be removed from the study database.

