3.0 Scientific Endpoints*

2.1 Describe the scientific endpoint(s), the main result or occurrence under study.

*NOTE: Scientific endpoints are outcomes defined before the study begins to determine whether the objectives of the study have been met and to draw conclusions from the data. Include primary and secondary endpoints. Some example endpoints are: reduction of symptoms, improvement in quality of life, or survival. Your response should **not** be a date.*

Response:

Primary Objective

Evaluate the safety of the intervention through 42 days of follow-up as compared to the control arm as assessed by:

- Cumulative incidence of serious adverse events (SAEs)
- Cumulative incidence of Grade 3 and 4 adverse events (AEs).

- Adverse Events of Special Interest
- Discontinuation or temporary suspension of the investigational medication (for any reason).

Secondary Objectives

Evaluate the clinical efficacy of melatonin as compared to placebo as assessed by:

Hospitalization: Incidence of COVID related hospitalization at 42 days.

Data will be obtained from electronic medical record.

COVID related symptoms: Fever, chills, cough, nasal symptoms, body aches/muscle aches, headache, loss of smell, loss of taste, nausea, vomiting, diarrhea, fatigue, dizziness. The speed of resolution of COVID related symptoms. Change from baseline, Day 1 to Day 42. Accessed by questionnarre.

Change in the WHO Clinical Progression Scale (0-10). Data will be obtained from electronic medical record.

Mortality: 42-day mortality. Data will be obtained from electronic medical record.

Exploratory Objective

Evaluate the effect of melatonin on virologic parameters as compared to placebo and assessed by:

-Percent of subjects with SARS-CoV-2 detectable in saliva sample at days 1, 3, 7, 14, 28 and 42.

-Quantitative RT-PCR for SARS-CoV-2 virus in saliva sample at days 1, 3, 7, 14, 28 and 42.

-Evaluate the reduction in cytokine/chemokine RNA and/or protein levels in saliva:

-Reduction as compared to baseline (Day 1) in salivary levels of cytokine/chemokine RNA and/or protein (IL-1, IL-2, IL-3, IL-4, IL-6, IL-8, IL-10, IL-11, IL-12, IL-13, IL-17, IL-18, TNF α , IFNy, IFN α , IFN-B, MCP1) at days 3, 7, 14, and 28.

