- Take the IP 3 times a day orally for 14 days.
- On Days 3, 7, 14, 28 and 42 collect a sample of saliva prior to taking drug in a collection container provided. Place the sample in a collection bag and place it in a freezer.
- Speak to the research coordinator through telemedicine on Days 3, 7, 14, 28 and 42 to provide

data as well as any adverse effects of the treatment. These include anxiety and depression and drowsiness special interest adverse events. The duration of these visits will be 15-30 minutes.

- Allow a courier to come to your house to collect study related materials on Day 15 ± 3 and day 43 ± 3 to pick up study related materials.

12.2 Describe what data will be collected.

NOTE: For studies with multiple data collection points or long-term follow up, consider the addition of a schedule or table in your response.

Response: Please see Table above

12.3 List any instruments or measurement tools used to collect data (e.g. questionnaire, interview guide, validated instrument, data collection form).

Include copies of these documents with your submission.

Response: Included documents: 1) Data collection form (baseline); 2) Data collection form (Follow-up); 3) Daily symptom questionnaire; 4) Body temperature and pulse oximetry logs; 5) Instructions for saliva collection, storage and shipping 6) WHO Clinical Progression Scale

12.4 Describe any source records that will be used to collect data about subjects (e.g. school records, electronic medical records).

Response: EMR data will be accessed to ascertain baseline health information and information relevant to the participants COVID illness. The study team will have remote access to the relevant EMRs.

12.5 Indicate whether or not **individual** subject results, such as results of investigational diagnostic tests, genetic tests, or incidental findings will be shared with subjects or others (e.g., the subject's primary care physician) and if so, describe how these will be shared.

Response: No

12.6 Indicate whether or not **study** results will be shared with subjects or others, and if so, describe how these will be shared.

Response: Study results will be posted on Clinical Trials.gov and submitted for publication in a peer reviewed journal.

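### Withdrawal by the study team (22.1–22.2), read as written, ends the scheduled safety calls before Day 42, so some later Grade 3/4 and non-hospitalized serious events may go unrecorded

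*Combined protocol and SAP*

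**What the plan says.** The primary objective in section 3.0 reads "Evaluate the safety of the intervention through 42 days of follow-up", with serious adverse events (SAEs), Grade 3/4 adverse events (AEs) and discontinuation or suspension of study medication among its measures. On collection, 21.4 states: "The safety information will be collected by scheduled phone calls as described above". Section 12.1 has subjects "Speak to the research coordinator through telemedicine on Days 3, 7, 14, 28 and 42", and 21.5 adds Day 1.

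The prompt to 22.1 asks when the team may remove a subject without the subject's agreement. Two grounds matter here. The first is an AE: "If they have adverse events that could be possibly related to Melatonin such that the study team think their continued participation is not advisable". The second is noncompliance: "If participants are noncompliant with the research procedures, there is the possibility they will be withdrawn from the research".

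For orderly termination, 22.2 says "An end of study visit will be conducted over the phone", followed by a courier pickup. Section 22.3 says "Subjects who withdraw from taking the study drug will be encouraged to stay in the study", gives the same closing phone visit to those who decline, and adds "Already collected data and samples will not be removed from the study database".

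Section 19.1 analyses subjects in their randomized arm, estimates each binary safety outcome by its relative frequency with a Clopper-Pearson interval, and imputes nothing. It recognizes that missingness may be informative and promises cautious interpretation.

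**The concern.** The safety outcomes need observation to Day 42, and the calls are the stated means of getting it. Withdrawal by the team leads only to a closing call. No passage says that the remaining calls, or checks of the EMR, go on afterwards. The template prompts to 22.2 and 22.3 raise safety follow-up and continued data collection, but the answers do not cover subjects whom the team removes.

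One of the two grounds is itself a safety event, so the loss of observation may be related to the outcome being estimated. If such a subject is then counted as event-free, the proportion can only be too low. Section 19.1 does not say whether a subject removed without an event is a non-event or leaves the denominator. The resulting proportions are meant to inform later comparative trials.

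**Working it through.** **1. The plan's own precision figure.** Inputs: 30 subjects (7.1) and 2:1 allocation (19.1), so 30 × 2/3 = 20 on melatonin and 30 × 1/3 = 10 on placebo. The maximum standard error on melatonin is √(0.5 × 0.5 / 20) = 0.1118, or 11.2 percentage points. This agrees, after rounding, with the 11 points in 19.2. The figure assumes that all 20 outcomes are known.

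**2. What follows each route out.**

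| Route | Stated consequence | Calls to Day 42? |
|---|---|---|
| Subject stops drug and stays | Encouraged to remain (22.3) | Yes |
| Subject stops drug and leaves | Closing phone visit, courier (22.3) | No |
| Team withdraws for AE | Closing phone visit, courier (22.2) | Not stated |
| Team withdraws for noncompliance | Closing phone visit, courier (22.2) | Not stated |

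If the last two rows end the calls, removal just after the Day 3 call forgoes four scheduled calls (Days 7, 14, 28, 42). Removal just after Day 7 forgoes three, and just after Day 14 forgoes two, with 42 − 14 = 28 days unobserved by telephone.

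**3. Who is affected.** A subject removed after an SAE or a Grade 3/4 AE already counts for that outcome, and one who stops drug counts as a discontinuation. What remains is a subject removed for a lower-grade AE or for noncompliance who later has a severe event that the EMR does not reveal.

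**4. Bound per subject.** Each such subject is either a non-event or an event: 1/20 = 5 points on melatonin, 1/10 = 10 points on placebo.

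**5. Effect on the estimates.** The documents give no withdrawal rate and no expected SAE or Grade 3/4 rate, so these counts are assumptions. Melatonin, two subjects removed event-free, Clopper-Pearson 95% limits:

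| Events seen in others | Counted as non-events | Dropped | Both had an event |
|---|---|---|---|
| 0 | 0/20 = 0% (0–16.8) | 0/18 = 0% (0–18.5) | 2/20 = 10.0% (1.2–31.7) |
| 4 | 4/20 = 20.0% (5.7–43.7) | 4/18 = 22.2% (6.4–47.6) | 6/20 = 30.0% (11.9–54.3) |

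Placebo, one removed event-free: 0/10 = 0% (0–30.8) against 1/10 = 10.0% (0.3–44.5), or 2/10 = 20.0% (2.5–55.6) against 3/10 = 30.0% (6.7–65.2).

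On melatonin the choice between non-event and dropped moves the estimate by 0 to 22.2 − 20.0 = 2.2 points. Dropping two subjects raises the maximum standard error to √(0.25/18) = 11.8 points. Unobserved events move the estimate by up to 2/20 = 10 points.

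**6. An illustrative expected loss.** Assume a true risk of 20%, with 25% to 75% of it falling after removal. Two removals then lose 2 × 0.20 × 0.25 = 0.1 to 2 × 0.20 × 0.75 = 0.3 events on average. Over 20 subjects that is 0.5 to 1.5 points. The chance of losing at least one event is 1 − (1 − 0.05)² = 9.8% to 1 − (1 − 0.15)² = 27.8%. This assumes that the EMR recovers nothing.

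**The case against.** The strongest reply is that this is an inference from silence. The AE sentence in 22.1 could mean stopping drug only, and 22.3 shows a general wish to keep off-drug subjects in the study. The consent form was not available for this review and may carry follow-up terms. This stands as a reason for caution. But the AE sentence answers a prompt about removal from the research and speaks of participation. The noncompliance sentence names withdrawal from the research outright.

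A reader might infer that all later SAEs would be lost. The documents do not support that. Section 3.0 takes COVID-related hospitalization and mortality at 42 days from the EMR, with no stated stop at withdrawal. Section 19.1 also analyses all-cause hospitalization, and the external reviewer in section 21 judges whether admissions were COVID related, which implies that other admissions are collected. Many SAEs could therefore be recovered. Even so, 12.4 describes EMR access in terms of baseline health and the COVID illness, and no passage ties it to AE capture in withdrawn subjects.

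A reader might also take 10 points as the likely error on melatonin. It requires two removals, each followed by an unrecorded event, while 23.1 expects the effects of melatonin to be mild. The illustrative expected loss is far smaller, and the interval at 4/20 is already about 38 points wide. Nor do the documents link lower-grade AEs to later severe ones, so informative loss is possible but not shown.

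Finally, subjects removed for noncompliance may not answer further calls, so not all of the loss can be avoided. The caution promised in 19.1 is proper, but it does not recover an event that nobody asked about.

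**Conclusion.** The point holds in limited form. Read as written, withdrawal by the team ends the scheduled safety calls before Day 42. The exposure is mainly later Grade 3/4 AEs, and SAEs without admission, in subjects removed before having such an event. The documents do not support a claim that earlier events are discarded or that randomized subjects leave their arm: 22.3 keeps the data and 19.1 keeps the assignment.

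The size is a worst-case bound of 5 points per such subject on melatonin and 10 on placebo. It rests on 20 and 10 randomized subjects, and the number of withdrawals is unknown. Continued follow-up matters more than the denominator wording. This is a cheap improvement, not a flaw that undermines the trial.

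**What to change.** **Sections 22.2–22.3.** Separate stopping study drug from stopping safety data collection. State that, after the team withdraws a randomized COVID-positive subject, the remaining scheduled safety calls and EMR checks continue to Day 42 unless the subject withdraws consent. Who stops drug, when and why stays as it is. If the consent form has follow-up terms, bring the two into line.

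**Section 19.1.** Keep all such randomized subjects in the denominator of the binary safety outcomes and count every recorded event. Report, by arm, the number without complete Day 42 follow-up. Add a simple sensitivity analysis in which all event-free subjects with incomplete follow-up are counted first as non-events and then as events.

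**Cost.** A few sentences of wording, plus a few calls and record checks within the existing schedule. Some withdrawn subjects, especially those removed for noncompliance, may not answer; for them the EMR checks and the bounds must serve.

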23.0 Risks to Subjects*

23.1 List the reasonably foreseeable risks, discomforts, hazards, or inconveniences to the subjects related to their participation in the research. Consider physical, psychological, social, legal, and economic risks. Include a description of the probability, magnitude, duration, and reversibility of the risks.

NOTE: Breach of confidentiality is always a risk for identifiable subject data.

Response:

Nasopharyngeal swabs are associated with discomfort that is usually short-lived.

Potential risks associated with the use of planned doses of melatonin include dizziness, headache, vivid dreams, nausea and sleepiness, that are anticipated to be of mild severity.

Breach of confidentiality is an associated risk of this research.

23.2 Describe procedures performed to lessen the probability or magnitude of risks, including procedures being performed to monitor subjects for safety.

Response: The frequent telephonic follow-up and the availability of the study team to the participants in case adverse effects arise.

Please see section 20.1 for procedures performed to lessen the risk of breach of confidentiality.

23.3 If applicable, indicate which procedures may have risks to the subjects that are currently unforeseeable.

Response: Melatonin has never been studied in COVID patients, therefore there are unforeseeable risks.

23.4 If applicable, indicate which research procedures may have risks to an embryo or fetus should the subject be or become pregnant.

Response: Melatonin has not been studied in pregnancy.

23.5 If applicable, describe risks to others who are not subjects.

Response: NA

24.0 Potential Benefits to Subjects*

24.1 Describe the potential benefits that individual subjects may experience by taking part in the research. Include the probability, magnitude, and duration of the potential benefits. Indicate if there is no direct benefit.

NOTE: Compensation cannot be stated as a benefit.

Response:

The candidate therapeutic(s) being evaluated may or may not improve clinical outcome of an individual adult subject with COVID-19 who participates in this trial. However, there is potential benefit to society from their participation in this study resulting from insights gained about the therapeutic agents under study as well as the natural history of the disease. While there may not be benefits for an individual subject, there may be benefits to society if a safe, efficacious therapeutic agent can be identified during this global COVID-19 outbreak.

The overall risk of using Melatonin in COVID is likely to be low and the potential benefit is high. This favorable risk-benefit ratio supports the conduct of this pilot study, and if the results of this pilot study are consistent with our expectations, a larger definitive trial.

